6.2. General Post Text Summary Table and Individual Subject Data Listing Format Considerations

Tables, listings, and figures will be numbered using a decimal system to indicate the main levels of unique displays and sub-levels of replicate displays. The first level represents the appendix within which the tables, figures, and listings will appear. This will be 14 for tables and figures and 16.2.x for listings. The second level of the numbering represents the type of data; 1 for study population, 2 for efficacy, 3 for safety, 4 for health outcomes, 5 for PK, and 6 for PD. The third level of numbering represents the type of endpoint within the data type, the fourth level represents a count of displays for the endpoint, and the fifth level is used for repeated tables. For example, tables may be repeated using a different population or for a subset of subjects.

Secondary titles will be used to identify the analysis population used for the displays.

In general, the listings should be sorted and presented by treatment assignment, subject number, and visit, if applicable. For Part 1, listings that include visit, visit date, and study day should be included on listings. For listings produced for the analysis at the end of Part 3 that include visit, displays should include visit, adjusted visit, visit date, study day, and adjusted study day.

6.3. Data Management

A data management plan will be developed and approved prior to commencement of data entry. Data will be captured using the Medidata electronic data capture system. Electronic validation steps (edit checks) will be utilized, and data cleaning will occur in conjunction with each site. Prior to transfer of data provided by vendors (eg, laboratory data), a data transfer agreement including specifications for the type of file, definitions of variables, and contact information for the sending and receiving parties will be developed and finalized. The standard operating procedures (SOPs) of PharPoint, the selected statistics and programming vendor for this study, will be used.

Data will be mapped to Study Data Tabulation Model (SDTM)-compliant datasets prior to creation of Analysis Data Model (ADaM)-compliant derived datasets for use in the creation of summary tables. All analyses will be generated using SAS v9.4 or higher and in accordance with PharPoint SOPs.

6.4. Data Presentation Conventions

Continuous variables (eg, age) are summarized using descriptive statistics (the number of subjects with available data, the mean, SD, median, and minimum and maximum). Categorical variables (eg, gender) are summarized using counts and percentages. Percentages are calculated using the total number of subjects per treatment group unless otherwise specified.

The following conventions are applied to all data presentations and summaries:

- For continuous variables, all mean and median values are formatted to 1 more decimal place than the measured value. SD values are formatted to 2 more decimal places than the measured value. Minimum and maximum values are presented with the same number of decimal places as the measured value.
- For categorical variables, the number and percentage of responses are presented in the form XX (XX.X%) where the percentage is in the parentheses.
- Date variables are formatted as DDMMMYYYY for presentation. Time is formatted in military time (24-hour clock) as HH:MM for presentation. Dates missing day are denoted as MMMYYYY and dates missing both day and month are denoted as YYYY in listings. Handling of partial dates for analysis is discussed in Section 6.8.
- Wherever possible, data will be decimal aligned.

The table of contents of statistical displays is provided in Section 17.1 as part of this SAP. Any changes to format, layout, titles, numbering, or any other minor deviation will not necessitate a revision to the SAP, nor will they be considered as deviations from planned analyses. Only true differences in the analysis methods or data handling will necessitate such documentation. The appropriate listings supporting the tables will be included and are not necessarily specified in the individual sections throughout the document.

6.5. Analysis Populations

6.5.1. Screen Failures

Subjects who give informed consent but are not randomized to study treatment and are noted as screen failures in the electronic case report form (eCRF) are considered screen failures. Reasons for screen failure will be summarized using this population.

6.5.2. Intent-to-Treat Population

The intent to treat (ITT) population will include all subjects who are randomized, regardless of whether study treatment was administered. The ITT population will be used as the primary population for efficacy and health outcomes analyses. Subjects will be analyzed based on the treatment to which they were randomized.

6.5.3. Safety Population

The safety population will include all subjects who received at least 1 capsule of study drug. This population will be used for all analyses of accountability, demographics, BCX7353 drug concentrations, and safety. Subjects will be analyzed based on the actual treatment received at first dose for all subjects for Part 1 or at first dose of Part 2 for subjects originally randomized to placebo. **Per-Protocol Population**

The per protocol (PP) population will include a subset of subjects in the safety population that complete Part 1 and have $\geq 85\%$ treatment compliance without any major protocol deviations that could impact efficacy measures. A decision will be made prior to database lock on which (if any) subjects are to be excluded from the PP population based upon major protocol deviations. In the PP analysis, subjects will be assessed based on the actual treatment received on study Day 1 for Part 1. The PP population may be used as a secondary population for efficacy analyses.

6.5.5. Completers Population

The subset of subjects in the ITT population who complete Part 1 of the study (as evidenced by the completion of the Week 24 visit in the eCRF) will comprise the completers population. The completers population will be used for a sensitivity analysis of the primary efficacy analysis for Part 1 only. Data will be analyzed according to randomized treatment. **Pharmacodynamic Population**

The PD population for plasma kallikrein inhibition will include all subjects for whom at least 1 pre- and post-dose plasma kallikrein inhibition result can be estimated. Data will be analyzed according to the actual treatment received. This population will be used for all analyses of plasma kallikrein inhibition.

6.5.7. Pharmacokinetic Concentration/Pharmacodynamic Population

The PK concentration/PD population will include all subjects for whom at least 1 pre- and post dose plasma kallikrein inhibition result can be estimated with a corresponding plasma BCX7353 concentration (placebo samples not analyzed will be assumed to have a zero concentration). This population will be used for all correlation analyses and figures involving plasma kallikrein inhibition and plasma BCX7353 concentrations.

6.6. Baseline Definition

In general, the baseline value is the last available assessment prior to the time of first dose of study drug unless otherwise specified. For tables that include adjusted visit information, the baseline for active treatment for subjects who originally were assigned to placebo will be the last available assessment prior to the time of first dose of active treatment in Part 2, unless otherwise specified.

6.6.1. Baseline Event Rate

Enrollment into treatment groups is stratified by the baseline HAE event rate as determined by the IXRS system based on the number of events and duration of screening as input by the sites (≥ 2 events/month vs. < 2 events/month). For analysis purposes, the baseline event rate will be calculated from the diary data and expressed as events per month where 1 month = 28 days as follows:

$$\frac{\text{Number of HAE events meeting baseline criteria from Screening to First Dose Date/time} * 28}{\text{Date of First Dose} - \text{Screening Date} + 1}$$

Criteria that must be met for events to qualify for confirmation by the Investigator during the baseline period are provided in Section 4.1.

Baseline event rate will be included in statistical models as appropriate.

6.6.2. Categorized Baseline Event Rate

The categorized baseline event rate will be determined using the calculated baseline event rate (See Section 6.6.1) and will be categorized similarly to the stratification factor: ≥ 2 events/month vs. < 2 events/month.

6.6.3. Baseline Age

Age at time of consent is collected on the demographics form. This will be the baseline age for analyses and for determination of whether the subject is classified as an adult (≥ 18 years) or an adolescent (12 to 17 years).

6.7. Derived and Transformed Data

6.7.1. Study Day

In this study, it is possible that the randomization date and date of first dose could differ. Study Day 1 is defined as the date of first dose.

If the date of measurement for a particular endpoint occurs on or after the first dose date, then study day will be calculated as (date of measurement – date of first dose) + 1. If the date of measurement occurs prior to the first dose date, then study day will be calculated as (date of measurement – date of first dose). There is no Day 0.

6.7.2. Change from Baseline

CFB is calculated as (post-baseline result – baseline result). Percent CFB is calculated as ((change from baseline/baseline result) * 100).

If either the baseline or the post-baseline result is missing, the CFB and/or percentage CFB is set to missing as well.

6.7.3. Visit Windows

For summary purposes in general, records will be assigned to the scheduled visit collected on the case report form (CRF). Unscheduled and early termination visits will be assigned to an analysis window according to the study day of the actual visit date using the visit windows displayed in [Table 10](#). All information collected at an unscheduled visit will be identified as such in the listings.

Table 10: Visit Windows (Days)

Visit	Relative Target Day	Protocol-Specified Visit Window	Analysis Visit Window
Screening visit		-70 to -14	-70 to -14
Baseline	1	1	1
Week 2	15	13 to 17	2 to 22
Week 4	29	27 to 31	23 to 43
Week 8	57	55 to 59	44 to 71
Week 12	85	83 to 87	72 to 106
Week 18	127	125 to 129	107 to 148
Week 24	169	169	149 to 176
Week 26	183	181 to 185	177 to 190
Week 28	197	195 to 199	191 to 211
Week 32	225	223 to 227	212 to 239
Week 36	253	251 to 255	240 to 295
Week 48	337	330 to 343	296 to 351
Week 52	365	364 to 368	352 to 406
Week 60	421	415 to 427	407 to 463
Week 72	505	499 to 511	464 to 547
Week 84	589	583 to 595	548 to 631
Week 96	673	667 to 679	632 to 683
Week 104	729	723 to 735	≥684

6.7.4. Multiple Assessments

Where multiple planned scheduled measurements are recorded for a given time point (eg, electrocardiograms [ECGs]), the mean of the measurements will be calculated and used in any derivation of summary statistics. All available data will be listed.

When multiple visits occur within the same window, the scheduled visit will be used in analysis if available. If no scheduled visit occurs within the window and an unscheduled visit(s) and/or

early termination visit occur within the window, the analysis visit closest to the target day will be selected for use in analysis. If deemed appropriate by the Sponsor (eg, in the case of a retest), unscheduled visits may be chosen for analysis given documentation of the desired visit from the Sponsor. Results from unscheduled visits will be eligible for inclusion in analyses of worst post-baseline results. Listings will display all visits as recorded on the CRF, including the date and study day. All available data including any totals, domains, or subscales of scale assessments summarized will be listed.

6.7.5. Derived Efficacy Endpoints

6.7.5.1. Event Rate

General Formula for Event Rate

In general, the formula for computing an event rate is the number of events meeting the event criteria divided by the duration of treatment during the reporting period of interest. Duration of treatment during the reporting period of interest = the last day in the reporting period – first day in the reporting period + 1.

$$\begin{aligned} \text{Event Rate} \left(\frac{\text{events}}{\text{month}} \right) \text{ During Reporting Period of Interest} \\ = \frac{\text{Number of Events} * 28}{\text{Duration of Treatment During Reporting Period in Days}} \end{aligned}$$

If the subject discontinues treatment early, any events that occur within 24 hours after last dose will be counted in the calculation of event rate and the additional 24-hour period will be included in the duration of the reporting period.

Subject-Reported Event Rate

Diary entries for events and investigator-collected events that are not captured in the diary are considered subject-reported events. The expert reviews each event and either confirms it as an event or rejects it as an event. For Part 3, there is no expert review of attacks, but an adjusted subject-reported attack rate will be computed based on a list of programmable requirements.

Subject-reported event rates will be computed for the entire dosing period only (ie, not for the effective dosing period or by month) for Parts 1, 2, and 3.

Adjusted Subject-Reported Attack Rate for Part 3

Because there is no expert-confirmation of attacks during Part 3, an adjusted subject-reported attack rate will be computed.

Subject-reported attacks must meet the following criteria (applied in order) for inclusion in the adjusted subject-reported rate computation:

- Attack must include at least 1 symptom of swelling
- Subject response to diary question, “In retrospect, could there be an alternative explanation for your symptoms other than an HAE attack (ie, allergic reaction, viral cold, etc)?” must be “no”

- Attack must be unique (attack begins > 24 hours from end of the prior attack), otherwise the event will be combined with and treated as a continuation of the preceding attack
- If untreated, attack must have a duration > 24 hours

Adjusted subject-reported attack rates will be computed for the following reporting periods and expressed in units of attacks/month where 1 month = 28 days:

- Part 3, by month
- Part 3, entire dosing period

For adjusted subject-reported attack rates by month, months will be defined in blocks of 28 days, beginning on the first day of dosing in Part 3. If the subject discontinues treatment early, any attacks that occur within 24 hours after last dose will be counted in the calculation of subject-reported adjusted attack rate and the additional 24 hour-period will be included in the duration of the reporting period.

Confirmed Event Rate

Confirmed event rates will be computed based on the number of expert-confirmed events that occur during the reporting period of interest.

Confirmed event rates will be computed for the following reporting periods and expressed in units of events/month where 1 month = 28 days:

- Parts 1 and 2, by month
- Parts 1 and 2, entire dosing period
- Parts 1 and 2, effective dosing period

Confirmed event rates will be computed for Part 1 and at the end of Part 2. For confirmed event rates by month, months will be defined in blocks of 28 days, beginning on Day 1, the day of first dose. The entire dosing period begins on Day 1 or adjusted Day 1 during Part 2 for subjects originally randomized to placebo. The effective dosing period similarly begins on Day 8 or adjusted Day 8. Part 1 continues until the time of Part 2 dose. Part 2 continues until the time of the first dose for Part 3. Expert confirmation is not done in Part 3 and so confirmed event rate will not be computed for Part 3. If the subject discontinues treatment early, the reporting period will continue through 24 hours post last dose and any events that occur within 24 hours after last dose will be counted in the calculation of events rate. If there are confirmed events in the eCRF without corresponding diary information, as may happen if a subject verbally reports an event to an investigator but does not enter it into the e-diary, the event will be counted.

For sensitivity analyses for missing data for the Part 1 primary analysis, confirmed event rates for the entire dosing period for subjects who discontinue treatment early will be re-computed as a weighted average of the observed post-treatment discontinuation event rate and an imputed event rate for periods of missing data post-treatment discontinuation. Details are provided in Section 6.8.1.

Expert-Confirmed Event Rate by Location

Expert-confirmed abdominal-only, peripheral, and mixed event rates will be computed using the location definitions provided in Section 6.7.5.9.

Adjusted Expert-Confirmed Event Rate

An adjusted expert-confirmed event rate will be computed for use in the determination of the 50%, 70%, and 90% responder endpoints comparing post-baseline event rates to baseline event rates. For the adjusted expert-confirmed event rate, the 2 additional requirements for confirmation of event rates used during screening will be applied to post-baseline expert-confirmed events to determine the number of confirmed events meeting the additional requirements. The additional requirements are:

- The events are unique, which is defined as an event that does not begin within 48 hours of the end of a previous event.
- The events must have either been treated, required medical attention or be documented to cause functional impairment based on subject entry in the diary. Functional impairment is defined as the subject being unable to perform their daily activities without restriction (ie, subject records that they are at least slightly restricted in their daily activities during their HAE event).

6.7.5.2. Number and Percentage of Subjects Who Are Event Free Over Entire Dosing Period and Effective Dosing Period

The following event-free endpoints will be derived for the entire dosing period and for the effective dosing period for Parts 1 and 2:

- The number and percentage of subjects with no confirmed events during the period of interest. Subjects with no confirmed events who discontinue before the end of the planned treatment period are not considered event-free.

The event-free rate for active treatment for subjects originally randomized to placebo will be based on the initial 24-week period during Part 2.

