7.1.9. Part 3 Secondary Endpoints

- Number and rate of angioedema events
- Durability of response (angioedema event rate trend over time)

- Number and proportion of days with angioedema symptoms
- Use of medications to treat angioedema events
- Durability in AE-QoL questionnaire scores
- Durability in EQ-5D-5L scores
- Durability in TSQM scores
- Durability in WPAI scores

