During the entire screening period (run-in period and the period after eligibility has been established during the run-in period but prior to randomization), angioedema events must meet the following stipulations to be counted in the baseline angioedema event rate calculation necessary for stratification, in addition to the expert confirmation:

- The angioedema events are unique, which is defined as an angioedema event that does not begin within 48 hours of the end of a previous angioedema event.
- The angioedema event must have either been treated, required medical attention, or be documented to cause functional impairment based on subject entry in the e-diary. Functional impairment is defined as the subject being unable to perform his or her daily activities without restriction (ie, subject records that he or she is at least slightly restricted in his or her daily activities during the angioedema event).
- The angioedema events must include symptoms of swelling. The expert will consider that symptoms of swelling, in addition to visible swelling, may also include symptoms in the oropharyngeal or abdominal regions that are indicative of internal swelling.

After randomization through the end of Part 2, the expert will use their judgment to confirm or reject a reported event as an angioedema event; however, all angioedema events must include symptoms of swelling. The expert will consider that symptoms of swelling, in addition to visible swelling, may also include symptoms in the oropharyngeal or abdominal regions that are indicative of internal swelling.

The selection of the independent expert(s) who will confirm or reject attacks will be made by the sponsor and may or may not be an investigator in the current study. Expert expectations for turn-around times of the event confirmation or rejection and how the event confirmation or rejection will be received by the investigator and site staff, especially in the period between screening and baseline, will be communicated separately.

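### The monthly attack-rate series changes definition at Week 52 with no common monthly measure, so a shift there cannot be cleanly attributed

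*SAP*

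**What the plan says.** Protocol 7.1.9 lists "Durability of response (angioedema event rate trend over time" among the Part 3 secondary endpoints; SAP 3.2.9 repeats it.

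**Parts 1 and 2.** Under Protocol 11.4.1.1, "the expert will use their judgment to confirm or reject a reported event as an angioedema event", and symptoms of swelling are mandatory. SAP 6.7.5.5 lets the expert count several subject-reported events as one. SAP 6.7.5.1 computes the confirmed rate by month for Parts 1 and 2 and states that it will not be computed for Part 3.

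**Part 3.** SAP 6.7.5.1 replaces it: "Because there is no expert-confirmation of attacks during Part 3, an adjusted subject-reported attack rate will be computed". An attack must show swelling, and the subject must answer no to the diary question about another explanation. The last two rules read "Attack must be unique (attack begins > 24 hours from end of the prior attack", failing which it is merged with the attack before it, and "If untreated, attack must have a duration > 24 hours". The reporting periods listed are "Part 3, by month" and the whole of Part 3.

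**Common measure.** The unadjusted subject-reported rate covers Parts 1, 2 and 3, but only for the entire dosing period ("ie, not for the effective dosing period or by month").

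**What else happens at Week 52.** Subjects on 110 mg move to open-label 150 mg (SAP 4.1, 5.2). In the tables they stay in their Part 2 treatment column with a footnote (SAP 6.1).

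**The concern.** A durability endpoint asks whether the response seen up to Week 52 was maintained afterwards. That needs an attack rate measured in the same way on both sides of Week 52. Here the outcome definition, the dose (for 110 mg subjects) and the blinding all change together, and no monthly measure crosses the boundary. If the monthly rate is lower or higher after Week 52, a reader cannot tell how much reflects counting rules, how much reflects dose, and how much reflects open-label reporting.

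Other Part 3 measures inherit the problem. Symptom-days come from expert-confirmed events in Parts 1 and 2 (SAP 6.7.5.3) but from adjusted events in Part 3 (SAP 17.1.1.1, table 14.2.5.1.1.P3). Part 3 event-free status (SAP 8.8.1) and use of HAE event medication (SAP 8.7.4) also rest on adjusted subject-reported attacks.

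**Working it through.** The plan states no figure on this point, so there is none to reproduce. The check is a comparison of definitions, followed by an illustration of scale.

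**Step 1. Definitions side by side** (Protocol 11.4.1.1 and 11.4.2.1; SAP 6.7.5.1 and 6.7.5.5)

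| Element | Parts 1 and 2 | Part 3 |
|---|---|---|
| Swelling | Required | Required |
| Another explanation | Expert may reject by judgment | Dropped unless the subject answers no to the diary question |
| Closely spaced events | Expert may combine | Always combined if the gap is 24 h or less |
| Untreated, 24 h or less | No stated rule | Dropped |
| Other expert rejection | Possible | None |
| Events reported outside the diary | Counted if confirmed in the eCRF | Investigator follow-up of events not required |
| Monthly rate | Confirmed rate only | Adjusted rate only |

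Three of the four programmed rules have some counterpart in Parts 1 and 2, fixed for swelling and discretionary for the other two. The duration rule for untreated attacks has none. It can only lower the Part 3 count. Loss of expert rejection can only raise it. The net sign is not determined by the documents.

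**Step 2. Is there a monthly bridge?** The output list (SAP 17.1) has adjusted subject-reported tables and figures with the .P3 suffix only. Table 14.2.2.1.ES is by month for the entire study, but it reports expert-confirmed events, which do not exist in Part 3. The subject-reported tables (14.2.1.18, .ES, .P3) are not monthly. The adjusted expert-confirmed rate for the responder endpoints uses a different rule set (48 h gap; treated, medical attention or impairment). So there is no bridge.

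**Step 3. Scale.** Inputs from Protocol 5.3.1, Study 302, per 28 days: 1.31 on 150 mg and 1.65 on 110 mg.

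Ratio = 1.31 / 1.65 = 0.794, a 20.6% lower rate.

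Let q be the net share of events lost through the change of definition. This is an assumption; the documents give no value. Further assume that the true dose effect equals the Study 302 ratio and that nothing else changes:

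- Subjects staying on 150 mg: apparent ratio = 1 − q
- Subjects moving from 110 to 150 mg: apparent ratio = 0.794 × (1 − q)

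| q (assumed) | 150 mg throughout | 110 to 150 mg |
|---|---|---|
| −0.10 (net gain) | 1.10 | 0.873 |
| 0 | 1.00 | 0.794 |
| 0.05 | 0.95 | 0.754 |
| 0.10 | 0.90 | 0.715 |
| 0.20 | 0.80 | 0.635 |
| 0.206 | 0.794 | 0.630 |
| 0.30 | 0.70 | 0.556 |

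At q = 0.206, subjects with no dose change would show a fall as large as the between-dose difference in Study 302. At q = −0.10 they would appear to lose response.

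**Step 4. What the 150 mg-throughout group can do.** Dividing the two columns gives 0.794 × (1 − q) / (1 − q) = 0.794. If q and any open-label effect are proportionally equal in both groups, comparing their shifts recovers the dose effect. It does not separate definition from open-label treatment. With the planned 24 subjects and no dropout, the groups would be 8 + 4 = 12 on 150 mg throughout and 8 + 4 = 12 switched, so the comparison is imprecise.

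**The case against.** The strongest case against has five parts.

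- **The SAP does not splice the series.** SAP 8.6.1 plots the Part 3 monthly rate separately and says why. The protocol foresaw rule-based confirmation in Part 3 (Protocol 11.4.2.1). Within Part 3 the definition is constant, and the Part 3 effectiveness objective covers Weeks 52 to 104. This stands, but it leaves the link back to the earlier response unmeasured.
- **The contrast between definitions is partial.** Experts may already merge events and may reject those with another cause. This stands.
- **Partial checks exist.** The 150 mg-throughout group and the whole-period subject-reported rate both allow a rough look at a level shift. This stands. Neither restores a monthly trend, and the first is small.
- **Treated events.** The duration rule applies only to untreated attacks, so rates of treated events are affected less. This stands.
- **Weight.** Hypothesis testing is confined to Part 1 (SAP 8.3), and the move to 150 mg rests on Study 302. This stands, and it limits the point to descriptive endpoints.

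A reader might infer that the Part 3 rule is simply stricter, so that the rate must fall at Week 52 and imitate a dose effect. The documents do not support that. Expert rejection is lost at the same time, which could raise the count. Protocol 5.1 describes symptoms typically subsiding over 3 to 5 days, which suggests that attacks of 24 h or less may be uncommon.

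**Conclusion.** The point holds as a gap in the measurement of durability. The monthly series changes definition at Week 52, the adjusted rate exists for Part 3 only, and no monthly rate is common to both sides. A level shift there cannot be cleanly divided between definition, the 110 to 150 mg change and open-label treatment.

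The size is unknown. The only benchmark is that a net loss of about 21% would equal the Study 302 between-dose difference; whether q is near that value, near zero or negative cannot be derived. It would also go too far to say that a dose effect cannot be examined at all, because the 150 mg-throughout subjects give a small internal comparison under the equal-q assumption.

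The consequence is confined to descriptive Part 3 secondary endpoints: the attack-rate trend, symptom-days and event-free status, and to a lesser degree treated events. The Part 1 primary analysis and the Part 3 primary safety endpoints are untouched. The change is worth making because it is cheap. The SAP already accepts the principle: for the responder endpoints it re-applies the screening criteria to post-baseline events so that both sides match.

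**What to change.** In SAP 6.7.5.1, add Parts 1 and 2 by month to the reporting periods of the adjusted subject-reported rate, derived with the Part 3 algorithm from the existing e-diary records. Then:

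- Report this rate by 28-day month across Parts 1 to 3 in one table and plot, beside the expert-confirmed rate for Parts 1 and 2. The overlap in Parts 1 and 2 measures the definitional effect directly.
- Show subjects on 150 mg throughout separately from those switched from 110 mg.
- Keep the expert-confirmed rate as the main measure for Parts 1 and 2.
- Use diary-entered events only in the common version, because investigator-collected events can enter the earlier counts.
- The documents do not show whether the alternative-explanation question was asked in Parts 1 and 2. If it was not, omit that rule from the common version and say so.
- Derive symptom-days and event-free status on the same basis.

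The cost is some extra programming and a few outputs; no new data are needed. One limit remains and should be stated: investigator follow-up of each event stops in Part 3, so ascertainment may still differ across Week 52 even under a common algorithm.
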